10.5.3.3 Laboratory abnormalities

Grading of laboratory values will be assigned programmatically as per NCI CTCAE version 4.03. The calculation of CTCAE v4.03 grades will be based on the observed laboratory values only, clinical assessments will not be taken into account.

CTCAE v4.03 Grade 0 will be assigned for all non-missing values not graded as 1 or higher. Grade 5 will not be applicable.

For laboratory tests where grades are not defined by CTCAE v4.03, results will be categorized as low/normal/high based on laboratory normal ranges.

The following listing/summaries will be generated separately for hematology, and biochemistry tests:

- Listing of all laboratory data with values flagged to show the corresponding CTCAE v4.03 grades if applicable and the classifications relative to the laboratory normal ranges

For laboratory tests where grades are defined by CTCAE v4.03

- Worst post-baseline CTCAE v4.03 grade (regardless of the baseline status). Each subject will be counted only once for the worst grade observed post-baseline.
- Shift tables using CTCAE v4.03 grades to compare baseline to the worst on-treatment value

For laboratory tests where grades are not defined by CTCAE v4.03,

- Shift tables using the low/normal/high/ (low and high) classification to compare baseline to the worst on-treatment value.

In addition to the above mentioned tables and listings, other exploratory analyses, for example figures plotting time course of raw or change in laboratory tests over time or box plots might be specified in the SAP.

10.5.3.4 Other safety data

Data from other tests, such as ECG and vital signs, will be listed and summarized accordingly. Notable values will be flagged in the listing. Definitions of notably abnormal results will be specified in the SAP.

ECG

12-lead ECGs including PR, QRS, QT, and QTcF intervals and heart rate will be obtained for each subject during the study. ECG data will be read and interpreted locally.

Categorical analysis of QT/QTc interval data based on the number of subjects meeting or exceeding predefined limits in terms of absolute QT/QTc intervals or changes from baseline will be presented. In addition, a listing of these subjects will be produced by treatment group.

Vital signs

Data on vital signs will be tabulated and listed, and notable values will be flagged.

10.5.3.5 Supportive analyses for secondary objectives

Not applicable.

10.5.3.6 Tolerability

Tolerability of study treatment will be assessed by summarizing the number of dose interruptions and dose reductions. Reasons for dose interruptions and dose reduction will be listed and summarized (see [Section 10.3](#)).

10.5.4 Pharmacokinetics

The respective PAS for each study drug will be used in the pharmacokinetic data analysis. Descriptive statistics (n, m (number of non-zero concentrations), mean, CV%, SD, median, geometric mean, geometric CV%, minimum and maximum) for PDR001, dabrafenib and trametinib concentrations will be presented at each scheduled time point by treatment. Pre-dose concentrations collected before dose administration on Day 1 of Cycle 2+ are C_{trough} for PDR001. In the cases where dosing of PDR001 starts at Cycle 2 only, C_{trough} are considered to be pre-dose concentrations collected before dose administration on Day 1 of Cycle 3+. Pre-dose concentrations collected before dose administration on Day 15 of Cycle 1+ are C_{trough} for dabrafenib and trametinib. All concentration data for PDR001, dabrafenib, and trametinib will be displayed graphically by treatment.

Following final PFS analysis data cut-off date 01-Jul-2020, PK samples will no longer be collected or sent to the central laboratory.

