Tumor (archival or new) tissue for central BRAF V600 mutation testing, [REDACTED] and potential companion diagnostic bridging study. Note: if local BRAF V600 mutation result is not available, sample will be used for screening and should be sent for central testing by Day -20	D	7.2.4.1.1	X																	
Optional newly acquired biopsy	D	7.2.4.1.2	X							X (anytime during Cycle 3)			Unscheduled: At disease progression and/or at a subsequent PD per response criteria for immunotherapy if subject continues treatment post progression, prior to the start of new antineoplastic therapy							

	Category	Protocol Section	Screening/Baseline	Treatment (Cycle = 28 days)									Follow-Up Period										
				Cycle 1			Cycle 2			Cycle 3		Subsequent Cycles Day 1	End of Study Treatment (EoT)	30- Day Safety Follow Up	60-Day Safety Follow Up	90-Day Safety Follow Up	120-Day Safety Follow Up	150 Day Safety Follow Up	End of Post Treatment Follow Up	Survival Follow Up			
Day of cycle			-28 to -1	1	8	15	1	8	15	1	15	1											

	Category	Protocol Section	Screening/Baseline	Treatment (Cycle = 28 days)									Follow-Up Period									
				Cycle 1			Cycle 2			Cycle 3			Subsequent Cycles Day 1	End of Study Treatment (EoT)	30- Day Safety Follow Up	60-Day Safety Follow Up	90-Day Safety Follow Up	120-Day Safety Follow Up	150 Day Safety Follow Up	End of Post Treatment Follow Up	Survival Follow Up	
Day of cycle			-28 to -1	1	8	15	1	8	15	1	15	1										
Study Administration																						
PDR001 infusion	D	6.1.1.1		DL1: PDR001 400mg IV every 4 weeks DL-1a: PDR001 400mg IV every 8 weeks DL-1b: at C2D1, PDR001 400mg IV every 4 weeks																		
Trametinib/Dabrafenib combination	D	6.1.1.1		Trametinib orally once daily and Dabrafenib orally twice daily for Days 1-28 of a 28-day cycle																		
PK sampling of PDR001 (for DL1 or DL-1a)	D	7.2.3.1.1		Following final PFS analysis data cut-off date 01-Jul-2020; PK and IG samples will no longer be collected or sent to central labs.																		
PK sampling of PDR001 (for DL-1b)	D	7.2.3.1.1																				
PK sampling of trametinib and dabrafenib	D	7.2.3.1.2																				
Immunogenicity (IG) sampling (For DL1 and DL-1a)	D	7.2.3.1.1																				
Immunogenicity (IG) sampling (for DL-1b)	D	7.2.3.1.1																				
Survival Follow-up	D	7.1.8																			X	

[figure not shown]
[figure not shown]
[figure not shown]

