7.2.3.1.1 Pharmacokinetic and immunogenicity (IG) sampling for PDR001

PK and IG blood sampling schedule for PDR001 is outlined in [Table 7-8](#) and [Table 7-9](#)

Table 7-8 Parts 1 & 2 Safety run-in and biomarker cohorts: Blood (serum) collection schedule for PDR001 PK and IG

Cycle	Day	Scheduled time point (hours)	Dose reference ID	PK Sample number	IG Sample number
1	1	Predose/0 hr ^a	1	101	201
1	1	End-of-Infusion ^a (within 2 hr)	1	102	
1	8	Anytime ^a	1	103	
1	15	Anytime ^a	1	104	
2	1	672 (±24h) hr / 0 hr pre-C2D1 dose	1/2 ^b	105	202
2	15	Anytime	2	106	
3	1	672 (±24h) hr / 0 hr pre-C3D1 dose	2/3 ^b	107	203
3	1	End-of-Infusion (within 2 hr)	3	108	
4	1	672 (±24h) hr / 0 hr pre-C4D1 dose	3/4 ^b	109	204
5	1	Predose/0 hr	5	110	205
6	1	Predose/0 hr	6	111	206
7	1	Predose/0 hr	7	112	207
8	1	Predose/0 hr	8	113	208
9	1	Predose/0 hr	9	114	209
10	1	Predose/0 hr	10	115	210
11	1	Predose/0 hr	11	116	211
12	1	Predose/0 hr	12	117	212
Every 6 Cycle after C12D1	1	Predose/0 hr	13+	118+	213+
EOT	-	Anytime	N/A	197	297
30-day safety follow-up visit ^c	-	Anytime	N/A	198	298
150-day safety follow-up visit ^c	-	Anytime	N/A	199	299
Unscheduled and at the time of progression or AE	N/A	Anytime	N/A	1001+	2001+

^a PK and immunogenicity samples for PDR001 will not be collected during Cycle 1 for the DL-1b dosing regimen during Part 1, or if DL-1b is the selected dosing regimen for Part 2, and at Cycle 1 Day 8 for Part 2.

^b The first Dose Reference ID (DRID) is for last dose the patient received prior to the collection of the PK sample, while the second DRID is for the current dose

^c If PDR001 is permanently discontinued prior to dabrafenib and/or trametinib, 30 day and 150 day safety follow up visits should be based on the last dose of PDR001.

- All predose samples must be collected within 30 min before the infusion begins
- An unscheduled PK samples and immunogenicity sample should be collected up on confirmed disease progression.
- Unscheduled PK and immunogenicity samples may be collected at any time if clinically indicated or at the Investigator's discretion and must be sequentially numbered as 1001, 1002, 1003, etc. for PK samples, and 2001, 2002, 2003, etc. for immunogenicity samples.
- After the primary Clinical Study Report (CSR) data cut-off date 01-Jul-2020 is reached, no additional PK and IG samples will be collected for the subjects still on-going on the study.

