7.2.3.1.2 Pharmacokinetic sampling for dabrafenib and trametinib

[figure not shown]
PK blood sampling schedule for dabrafenib and trametinib is outlined in [Table 7-10](#).

Table 7-10 Part 1 & 2 Safety run-in and biomarker cohorts: Pharmacokinetic blood (plasma) collection schedule for trametinib and dabrafenib

Cycle	Day	Scheduled time point (hours)	Trametinib Dose reference ID	Dabrafenib Dose reference ID	Trametinib Dose reference ID	Dabrafenib Dose reference ID	PK Sample number
			Refers to the last dose taken before PK collection		Refers to the dose taken on the day of PK collection		
1	1	Predose/0 hr			31	61	701
1	15	Predose/0 hr	321	621	32	62	702
1	15	Between 1 and 3 hr post-dose			32	62	703
2	1	Predose/0 hr	331	631	33	63	704
2	15	Predose/0 hr	341	641	34	64	705
3	1	Predose/0 hr	351	651	35	65	706
3	1	Between 2 and 12 hr post-dose			35	65	707
4	1	Predose/0hr	361	661	36	66	708
4	1	Between 2 and 12 hr post-dose			36	66	709
5	1	Predose/0 hr	371	671	37	67	710
6	1	Predose/0 hr	381	681	38	68	711
7	1	Predose/0 hr	391	691	39	69	712
8	1	Predose/0 hr	401	701	40	70	713
9	1	Predose/0 hr	411	711	41	71	714
10	1	Predose/0 hr	421	721	42	72	715
11	1	Predose/0 hr	431	731	43	73	716
12	1	Predose/0 hr	441	741	44	74	717
Every 6 Cycle after C12D1	1	Predose/0 hr	451+	751+	45+	75+	718+
EOT	1	Anytime	N/A	N/A	N/A	N/A	799
Unscheduled	N/A	Anytime	N/A	N/A	N/A	N/A	7001+

- All predose samples must be collected prior to dosing on PK day. For pre-dose samples, the date and time of the last dose taken before PK collection and the date and time of the first dose taken after PK collection should be recorded in Dose Administration Record (DAR) for dabrafenib and trametinib CRF page. An unscheduled PK sample should be collected up on confirmed disease progression.
- Unscheduled PK sample may be collected at any time if clinically indicated or at the Investigator's discretion and must be sequentially numbered as 7001, 7002, 7003, etc.
- After the primary CSR data cut-off date 01-Jul-2020 is reached, no additional PK samples will be collected for the subjects still on-going on the study.

**Table 7-11 Part 3 Double-blind, randomized, placebo-controlled part:
Pharmacokinetic blood (plasma) collection schedule for trametinib
and dabrafenib**

[figure not shown]
Cycle	Day	Scheduled time point (hours)	Trametinib Dose reference ID	Dabrafenib Dose reference ID	Trametinib Dose reference ID	Dabrafenib Dose reference ID	PK Sample number

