			Refers to the last dose taken before PK collection		Refers to the dose taken on the day of PK collection		
1	1	Predose/0 hr			31	61	801
2	1	Predose/0 hr	321	621	32	62	802
2	1	Between 1 and 3 hr post-dose			32	62	803
3	1	Predose/0 hr	331	631	33	63	804
3	1	Between 2 and 12 hr post-dose			33	63	805
4	1	Predose/0 hr	341	641	34	64	806
4	1	Between 2 and 12 hr post-dose			34	64	807
5	1	Predose/0 hr	351	651	35	65	808
6	1	Predose/0 hr	361	661	36	66	809
7	1	Predose/0 hr	371	671	37	67	810
8	1	Predose/0 hr	381	681	38	68	811
9	1	Predose/0 hr	391	691	39	69	812
10	1	Predose/0 hr	401	701	40	70	813
11	1	Predose/0 hr	411	711	41	71	814
12	1	Predose/0 hr	421	721	42	72	815
Every 6 Cycle after C12D1	1	Predose/0 hr	431+	731+	43+	73+	816+
EOT	1	Anytime	N/A	N/A	N/A	N/A	899
Unscheduled	N/A	Anytime	N/A	N/A	N/A	N/A	8001+

- All predose samples must be collected prior to dosing on PK day. For pre-dose samples, the date and time of the last dose taken before PK collection and the date and time of the first dose taken after PK collection should be recorded in DAR for dabrafenib and trametinib CRF page. An unscheduled PK sample should be collected up on confirmed disease progression.
- Unscheduled PK sample may be collected at any time if clinically indicated or at the Investigator's discretion and must be sequentially numbered as 3001, 3002, 3003, etc.
- After the primary CSR data cut-off date 01-Jul-2020 is reached, no additional PK samples will be collected for the subjects still on-going on the study.

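### The Ctrough rule in Section 10.5.4 is tied to visit days that do not fit the sampling tables: it is ambiguous for dabrafenib and trametinib, and it counts mid-interval PDR001 samples as troughs under DL-1a

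*Protocol*

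**What the plan says.** Section 10.5.4 of the protocol fixes Ctrough by visit day, in three statements:

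- PDR001: "Pre-dose concentrations collected before dose administration on Day 1 of Cycle 2+ are" troughs.
- PDR001, exception: "In the cases where dosing of PDR001 starts at Cycle 2 only", the troughs begin at Day 1 of Cycle 3.
- Dabrafenib and trametinib: "Pre-dose concentrations collected before dose administration on Day 15 of Cycle 1+ are" troughs. No distinction is made between study parts.

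The sampling tables are in Section 7.2.3.1. The Part 3 schedule for dabrafenib and trametinib ("Table 7-11 Part 3 Double-blind, randomized, placebo-controlled part") lists Day 1 of Cycles 1 to 12 and then "Every 6 Cycle after C12D1", again on Day 1. Its footnote requires that "All predose samples must be collected prior to dosing on PK day". Table 7-10, for Parts 1 and 2, adds Day 15 pre-dose samples at Cycles 1 and 2 only.

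For PDR001, Tables 7-8 and 7-9 schedule a pre-dose sample on Day 1 of every cycle from 2 to 12. Table 7-8 labels the Cycle 2 sample "672 (±24h) hr / 0 hr pre-C2D1 dose". Tables 7-1 and 7-3 both list the reduced-frequency option "DL-1a: PDR001 400mg IV every 8 weeks".

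**The concern.** A rule that defines a PK parameter by visit day has to match the visits at which samples are drawn. Here two mismatches appear.

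First, the dabrafenib and trametinib rule names Day 15, a day on which Part 3 draws no PK sample. Part 3 does have Day 15 visits in Cycles 1 and 2 (Section 7.1.3), but Table 7-11 takes no blood for PK at them.

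Second, the PDR001 rule assumes an infusion on Day 1 of each cycle. DL-1a is dosed every second cycle, so half of the dosing-interval positions that the rule calls trough are not the end of an interval.

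Comparing the arms on pharmacokinetics is a Part 3 secondary objective (Sections 10.5 and 10.5.2), and Part 3 gives the only randomised comparison of dabrafenib and trametinib levels with and without PDR001. PK data are also one input to regimen choice (Sections 10.4.2 and 10.7). Two programmers applying Section 10.5.4 could produce different Ctrough tables from the same data.

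**Working it through.** The protocol gives no figure to reproduce. The check counts scheduled pre-dose samples against the rule, with 28-day cycles.

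**Dabrafenib and trametinib, pre-dose samples after the first dose, through Cycle 12**

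- Table 7-10 (Parts 1 and 2): C1D15, C2D1, C2D15, then Day 1 of Cycles 3 to 12. Total 3 + 10 = 13.
- Table 7-11 (Part 3): Day 1 of Cycles 2 to 12. Total 11.

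| Reading of the rule | Parts 1 and 2 | Part 3 |
|---|---|---|
| Day 15 of each cycle from Cycle 1 | 2 of 13 (C1D15, C2D15) | 0 of 11 |
| Everything from C1D15 onward | 13 of 13 | 11 of 11 |

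After Cycle 12 all scheduled pre-dose samples in both tables are on Day 1, so the first reading selects none of them.

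**PDR001 under DL-1a**

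- Dosing interval: 8 weeks × 7 × 24 = 1344 h, or two cycles. Infusions therefore fall on Day 1 of Cycles 1, 3, 5 and so on, if given on schedule.
- Samples that the rule labels Ctrough: Day 1 of Cycles 2 to 12, 11 in all.
- Samples with no infusion at that visit: Cycles 2, 4, 6, 8, 10 and 12. That is 6 of 11 (54.5%), each 672 h into a 1344 h interval.
- Samples at the end of an interval: Cycles 3, 5, 7, 9 and 11, which is 5 of 11.
- Later samples (Cycles 18, 24, ...) are all in even cycles. The mid-interval share is 7 of 12 (58%) through Cycle 18 and 8 of 13 (62%) through Cycle 24.

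**Do other passages repair this?**

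- Table 7-8 gives the Cycle 2 sample dose reference ID 1/2, and the IDs rise with each cycle to 12 at Cycle 12. Table 7-9 does the same. Under DL-1a only 6 infusions would be scheduled by Cycle 12 (Cycles 1, 3, 5, 7, 9, 11).
- Table 7-8 labels the Cycle 3 Day 1 sample as 672 h. Under DL-1a it would be 1344 h after the previous infusion.
- Footnotes to both tables adapt them for DL-1b. Neither has one for DL-1a.
- The evaluability rule in Section 10.1.5 asks only that a pre-dose sample precede the next dose. A Cycle 2 Day 1 sample under DL-1a does so and is kept.
- Elsewhere the protocol does adapt: Table 7-7 places the post-infusion ECG at Cycle 2 for DL1 but at Cycle 3 for DL-1a and DL-1b.

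**The case against.** The strongest reply is that the Day 15 wording means from Cycle 1 Day 15 onward. That reading fits both tables: C1D15 is the first pre-dose sample after the first dose in Table 7-10, and it leaves no gap in Part 3. The parallel with the PDR001 sentence does not settle the matter, because all scheduled pre-dose PDR001 samples are on Day 1 and the two readings select the same ones there. This stands, and it means the first part of the point is ambiguity rather than a proven gap.

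A reader might infer that Part 3 has no usable dabrafenib or trametinib trough data, or that the PK objective is lost. The documents do not support that. Section 10.5.4 summarises concentrations at each scheduled time point by treatment and displays them all graphically. The population PK work in Section 10.5.4.2 models the concentrations and does not depend on the label.

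A reader might also infer that Part 3 is the only place to compare dabrafenib and trametinib levels with and without PDR001. It is the only randomised one. DL-1b, if opened, has a 4-week run-in without PDR001 and allows a within-subject comparison.

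On DL-1a, it can be said that a sample at a visit without an infusion is not taken before a dose, so a strict reader would exclude it, and that actual dose and draw times are recorded (Section 7.2.3.1). That has some force, but Tables 7-8 and 7-9 call these samples pre-dose without a DL-1a exception. It is also true that DL-1a opens only if regimen 1 is not tolerated (Section 14.2.3.5), and the part of the protocol at hand does not say whether it was used.

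Finally, one might try to turn the approximate Q8W-to-Q4W dose equivalence under Table 14-17 into a mid-interval-to-trough ratio. The protocol attributes that equivalence only to PK simulations, without stating the basis or a half-life, so no ratio can be derived from it without outside assumptions.

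**Conclusion.** The point holds as a minor error of definition. For dabrafenib and trametinib, Section 10.5.4 supports two readings that give 0 or 11 Part 3 troughs per subject through Cycle 12, and 2 or 13 in Parts 1 and 2. For PDR001, the rule together with Tables 7-8 and 7-9 labels 6 of 11 DL-1a samples through Cycle 12 as trough when they are mid-interval. This assumes infusions on schedule, and it matters only if DL-1a was used.

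The consequence is confined to what is reported as Ctrough. No concentration data are lost, and the primary and key secondary analyses are unaffected. PK sampling ended with the 01-Jul-2020 cut-off, so the correction concerns analysis and reporting of samples already collected.

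**What to change.** In Section 10.5.4:

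- Define dabrafenib and trametinib Ctrough as all pre-dose samples from C1D15 onward. Spell this out by part: C1D15, C2D15 and Day 1 of Cycle 2 and later in Parts 1 and 2, and Day 1 of Cycle 2 and later in Part 3.
- Define PDR001 Ctrough as samples taken just before an actual PDR001 infusion that ends a dosing interval, identified from dosing records. A rule based on records also copes with delayed infusions, which a list of odd cycles would not.
- Report DL-1a samples at visits without an infusion separately, as mid-interval.

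In both Table 7-8 and Table 7-9, reconcile the time-point labels and dose reference IDs with 8-weekly dosing for DL-1a.

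The cost is wording and a small change to the Ctrough derivation. No extra samples and no change to dosing are involved.

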10.5.4.1 Data handling principles

Missing values for any PK parameters or concentrations will not be imputed and will be treated as missing.

Below the limit of quantitation (BLQ) values will be set to zero by the Bioanalyst, and will be displayed in the listings as zero and flagged. BLQ values will be treated as missing for the calculation of the geometric means and geometric CV%.

10.5.4.2 Population pharmacokinetic analysis

The pharmacokinetics of dabrafenib and trametinib will be determined using a non-linear mixed effects modeling approach. Population pharmacokinetic parameters including CL/F, V/F, and absorption rate constant (k_a) will be estimated, if data permit. Dependent on the final structural pharmacokinetic model, additional pharmacokinetic parameters may also be estimated. Sources of variability in pharmacokinetic parameters will be investigated during population modeling.

If data permit, a mixed-effects model may be applied to the serum PDR001 concentration-time data to generate *post hoc* estimates of pharmacokinetic parameters using NONMEM to characterize PDR001 exposure in subjects with advanced melanoma.

[figure not shown]
If there are sufficient data for analysis, the details of the population pharmacokinetic analyses will be provided in a separate SAP, and the results may be reported in a separate population pharmacokinetic report. Data from this and other studies may be pooled for analysis.

10.5.5 Immunogenicity

[figure not shown]
Immunogenicity will be characterized descriptively by tabulating ADA prevalence at baseline and ADA incidence on-treatment.

Following final PFS analysis data cut-off date 01-Jul-2020, IG samples will no longer be collected or sent to the central laboratory.

10.5.6 Biomarkers

There may be circumstances when a decision is made to stop sample collection, or not perform or discontinue the analysis of blood / archival tumor samples / fresh tumor biopsies due to either practical or strategic reasons (e.g., issues related to the quality and/or quantity of the samples or issues related to the assay). Under such circumstances, the number of samples may be inadequate to perform a rigorous data analysis and the available data will only be listed and potentially summarized.

10.5.6.1 Outline of the data analysis

[REDACTED]
Additional analyses that may be performed after the completion of the end-of-study CSR will be documented in separate reports. These analyses may include but are not limited to the meta-analysis of data from this study combined with data from other studies [REDACTED]

[REDACTED] The data analysis will be described in an addendum of the SAP or in a stand-alone SAP document, as appropriate.

10.5.6.2 Data handling principles

Data preprocessing and transformations will be described in detail in the Programming Dataset Specifications document.

10.5.6.3 Data analysis principles

10.5.6.3.1 Analysis sets

Unless otherwise specified, all statistical analyses of biomarker data will be performed on subjects with biomarker data.

10.5.6.3.2 Basic tables, figures and listings

Unless otherwise stated, as project standard, all biomarker data collected will be listed and summarized [REDACTED]

Depending on the endpoint of interest, graphical displays such as box plots or strip plots may be used to assess the relationship of different biomarkers with clinical benefit. These may be separated by treatment cohort and include either baseline or change from baseline values, where applicable.

For categorical markers such as mutation status, 2x2 contingency tables may be used to assess the relationship with clinical benefit and or Kaplan – Meier curves may be generated given the number of PFS events warrant such an assessment.

